#### *Medical Record Data*

Research staff extracted medical, surgical, and demographic information was extracted from participants' electronic health records (EHR) using an investigator-developed abstraction tool. Data abstracted included demographic data (gender, age, race/ethnicity), medical data (height, weight, body mass index, comorbidities such as diabetes, hypertension, peripheral vascular disease and, smoking status, medical diagnoses, Braden Scale for predicting Pressure Sores (Braden) score, use of any PrI preventive strategies such as support surface use, repositioning schedules), surgery type, surgery length, use of vibration machines or other instruments in surgery, length of time in PAR unit, anesthesia used, use of vasopressors during surgery, estimated blood loss, volume of fluids provided during surgery, blood pressure during

surgery, American Society of Anesthesiologists physical status score and documentation of any skin damage. Using EHR data, a Scott-Triggers IAPrI risk assessment score was calculated for each participant. The Scott-Triggers tool examines four characteristics: age 62 years or older; albumin less than 3.5mg/dL or BMI less than 19 or greater than 40; American Society of Anesthesiologists physical status classification system (ASA) 3 or greater; and estimated surgery time over 3 hours. Each characteristic affirmed scores a point and scores greater than 1 indicate high risk for IAPrIs (37).

### **Study Analysis Plan**

The two outcome measures, IAPrI incidence by visual assessment and SEM Deltas indicative of PrI, were compared between participants undergoing prone surgery with standard care (no dressings, pressure reduction positioning on the operating table) and those with standard care and the intervention (use of MFSF dressings placed on chest, iliac crest, and face). Using Fisher's Exact test statistics, the percent of participants with IAPrI on face, chest, and iliac crest as defined above were compared between the two groups for initial post-operative assessment and postoperative days 2 and 3 assessments. There were insufficient participants to evaluate postoperative days 4 and 5.

Using binary logistic regression analyses, demographic, medical and surgical factors were compared for prospective participants who did and did not develop skin damage or IAPrIs controlling for group. Factors that increase risk for IAPrIs were evaluated including: hospital length of stay, surgery length, body mass index (BMI), and skin tone. Cochran Mantel-Haenszel statistics were used to compare the groups.

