### *Skin Assessments*

On the day of surgery, research staff obtained written HIPAA consent from participants and confirmed consent to participate in the study. Research staff collected visual skin assessment and sub-epidermal (SEM) measures for all participants at the anterior chin, upper cheeks, mid forehead (face), right and left upper chest above nipple line, and iliac crest, both pre-operatively in the Pre-Post Anesthesia Care Unit (PACU) and post-operatively in the PACU or after transfer to the floor unit. Once the pre-operative assessments were completed for intervention participants, research staff placed the multidimensionally flexible silicone foam (MFSF) dressings to the face (chin, cheeks, forehead), chest and iliac crest. Following surgery, research staff removed the MFSF dressings in the PACU or on transfer to the floor unit and then visual skin assessment and SEM measures were obtained. For all participants, visual skin assessments

and SEM measures were obtained daily on the floor unit until post-operative day five or discharge from hospital (whichever occurred first).

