device transmits high-frequency, low-power electromagnetic waves of 32 kHz via an electrode that requires light skin touch. In the skin, the induced electrical field interacts mainly with water molecules closest to the electrode, with depth of interaction depending on the diameter of the circular electrode (in this study depth was 4 mm). The portion of electromagnetic energy that is not absorbed by tissue water is reflected and measured by the device and displayed in three seconds in the measuring unit picoFarads (pF) (range, 0-7 pF). The electrical properties of free and bound water are nearly identical and thus the measure is reflective of total water content in the tissue.

*Definition Intraoperative Acquired PrIs.* Intraoperative acquired PrI (IAPrI) was defined two ways for each anatomic location. First, as erythema/skin discoloration of minimal or greater severity by visual skin assessment. Second, by calculating the difference between pre-operative and the post-operative SEM value (hereafter SEM Delta); SEM Deltas greater than or equal to 0.6pF were considered indicative of IAPrIs.

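### The SEM outcome is compared between groups without adjusting for pre-operative SEM, which costs some precision and leaves the comparison exposed to chance baseline imbalance

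*Combined protocol and SAP*

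**What the plan says.** SEM is measured at each site "both pre-operatively in the Pre-Post Anesthesia Care Unit (PACU) and post-operatively in the PACU or after transfer to the floor unit". The pre-operative reading is taken before treatment: "Once the pre-operative assessments were completed for intervention participants, research staff placed" the dressings (Skin Assessments).

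The SEM outcome is then built from that reading, "by calculating the difference between pre-operative and the post-operative SEM value (hereafter SEM Delta"), with the rule that "SEM Deltas greater than or equal to 0.6pF were considered indicative of IAPrIs" (Definition Intraoperative Acquired PrIs). I read Delta as post-operative minus pre-operative.

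The Study Analysis Plan gives the test: "Using Fisher's Exact test statistics, the percent of participants with IAPrI on face, chest, and iliac crest as defined above were compared". These regional percentages "were compared between the two groups for initial post-operative assessment and postoperative days 2 and 3 assessments". Two further analyses are mentioned:

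- Logistic models look for risk factors while controlling for group. The factors named are length of stay, surgery length, BMI and skin tone.
- Cochran Mantel-Haenszel statistics compare the groups, with no strata given.

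Pre-operative SEM is not named as a covariate or stratum in either. The text available describes no allocation method.

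**The concern.** The pre-operative value enters the analysis only by subtraction. When the pre/post correlation is below 1, a low first reading tends to be followed by a rise and a high one by a fall. The chance of crossing +0.6 pF therefore depends on where a participant starts, and the planned test ignores this.

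Two things are at stake. The test leaves out a measured, pre-treatment covariate that is tied to the outcome by construction, so it is less precise than it could be. And if the groups happen to differ in pre-operative SEM, part of that difference can carry into the percentages with SEM-defined IAPrI.

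**Working it through.** The plan gives no sample size, alpha, SD, event rate or correlation, so there is no figure to reproduce.

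**From the documents:** cut-off 0.6 pF; device reading in the "measuring unit picoFarads (pF) (range, 0-7 pF").

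**Assumed:** pre- and post-operative SEM bivariate normal with equal SD s = 0.6 pF; control mean rise m = 0.3 pF; correlation r = 0.5 (range 0.3 to 0.7); 50 or 100 per group; two-sided 0.05; one site per participant.

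**1. Delta depends on baseline.** corr(Delta, pre) = −√((1−r)/2), which is −0.59, −0.50 and −0.39 at r = 0.3, 0.5 and 0.7.

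For a participant z SDs from the mean baseline, P(Delta ≥ 0.6) = 1 − Φ((0.6 − m + (1−r)·s·z)/(s√(1−r²))). At r = 0.5 the denominator is 0.6 × √0.75 = 0.520.

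- z = −1: (0.3 − 0.3)/0.520 = 0, giving 50%.
- z = +1: (0.3 + 0.3)/0.520 = 1.15, giving 12%.
- Overall: the SD of Delta is s√(2(1−r)) = 0.6, so 0.3/0.6 = 0.5, giving 31%.

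With a mean rise of 0.2 pF the three figures are 42%, 9% and 25%.

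**2. Precision.** For a continuous outcome, the variance of the baseline-adjusted comparison relative to the change score is (1+r)/2: 0.65, 0.75 and 0.85 at r = 0.3, 0.5 and 0.7. The gain for the binary outcome was simulated with balanced baselines, a true 0.25 pF reduction and 100 per group. Power at r = 0.5:

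| Test of Delta ≥ 0.6 pF | Power |
|---|---|
| Fisher's exact | 51% |
| Unadjusted logistic (likelihood ratio) | 58% |
| Baseline-adjusted logistic (likelihood ratio) | 65% |

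Adjustment alone adds 65 − 58 = 7 points (11 at r = 0.3, 2 at r = 0.7). The other 58 − 51 = 7 points are Fisher's conservatism, a separate matter.

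**3. Chance imbalance under random allocation.** The SD of the difference in mean baseline is s√(2/n): 0.12 pF at 50 per group and 0.085 pF at 100. With no dressing effect and a dressing-group baseline higher by d, P(Delta ≥ 0.6) in that group is 1 − Φ((0.6 − m + (1−r)d)/0.6).

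- d = 0.12 pF (one SD of chance imbalance at 50 per group): 0.36/0.6 = 0.60, giving 27% against 31%.
- d = 0.30 pF (half an SD of SEM): 0.45/0.6 = 0.75, giving 23% against 31%. Fisher then rejects a true null in about 11% of trials at 50 per group and 20% at 100; the adjusted test stays near 5%.

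An imbalance of 0.30 pF or more in either direction is rare under randomisation: 0.30/0.12 = 2.5, probability about 1.2% at 50 per group; 0.30/0.085 = 3.5, about 0.04% at 100. With no systematic imbalance, Fisher's error rate is about 3 to 4%.

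**4. Groups with stable different SEM levels.** Take the same 0.30 pF difference, but let each group regress to its own mean. Delta then has the same distribution in both groups, 31% each. In simulation at r = 0.5 Fisher rejects a true null in about 3 to 5% of trials. The baseline-adjusted logistic test rejects in roughly 18 to 19% at 50 per group and 28 to 33% at 100.

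**The case against.** A reader might infer that regression to the mean makes the planned test biased in a predictable direction, and that adjusting for baseline removes the bias. The documents do not support this. Under random allocation there is no bias on average, and the 11% and 20% error rates are conditional on an imbalance that would seldom occur. Without random allocation, the result depends on whether the groups share one regression line. Step 4 shows the unadjusted test holding its level while the adjusted one fails. The documents do not settle which case applies. They describe no allocation method, but front matter was removed from the copy reviewed, so non-random allocation cannot be asserted either.

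Three further objections have force:

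- The power gain is modest and rests on a correlation that the plan does not give. In a separate one-site simulation (SD 0.5 pF, r = 0.5, rise 0.2 pF, 50 per group, true reduction 0.25 pF), most of the power loss came from the cut-off and Fisher's test: 24% for Fisher against 70% for a t-test on continuous Delta. Baseline adjustment moved the binary analysis only from 36% to 42%.
- The calculation uses one site. The face has four, and the plan does not say how site-level Deltas form a regional outcome, so the gain for a region may differ.
- The plan is written in the past tense. A new lead test may be a post hoc change, and Fisher's test is a defensible choice when events are few.

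These limit the size of the point and shape the remedy. They do not remove the omission: a baseline measured in everyone and correlated with the outcome is not used as a covariate.

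**Conclusion.** The point stands as one of precision and of protection against chance imbalance, for the SEM outcome only. The only specified test of that outcome between groups is unadjusted, and no other analysis names pre-operative SEM.

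Under the assumptions stated (SD 0.6 pF, rise 0.3 pF, true reduction 0.25 pF, 100 per group, one site), adjustment alone is worth about 2 to 11 power points over correlations of 0.7 to 0.3. A typical chance imbalance at 50 per group would shift one group's percentage by about 4 points at r = 0.5 (31% to 27%). The real size is unknown because the documents give none of the inputs.

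It does not follow that the planned comparison is biased, or that the adjusted one would be unbiased. If allocation was not random, neither is guaranteed to be. The change is worth making because the covariate is already collected.

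**What to change.** Keep the Delta ≥ 0.6 pF outcome, state how it is formed for each region, and state how participants were allocated. Then:

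1. For each region and assessment, add a logistic regression of the region's SEM outcome on group and pre-operative SEM for that region. Report the baseline-standardised risk difference with a 95% CI.
2. Where events are sparse, use penalised likelihood or an exact Cochran Mantel-Haenszel test stratified by pre-operative SEM.
3. If allocation was random, make this the lead SEM analysis. Otherwise report it beside the unadjusted Fisher result with equal prominence, and say that the two can disagree when the groups' SEM levels differ stably.
4. In either case, keep the Fisher result, tabulate pre-operative SEM by group, and label the adjusted analysis as added after the plan if it is.

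The cost is SAP wording and a few lines of code, with no new data. The downside is one extra parameter per model and possible fitting problems where events are few. The visual-assessment comparison is unaffected.

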*Visual Skin Assessment.* Trained research staff assessed skin health through direct independent visual assessments. Eight anatomic locations were assessed: mid forehead, chin, and right and left upper cheek, upper chest above nipple line and iliac crest. Areas of visual skin discoloration were palpated for blanchability in persons with light skin tones and any pressure injuries (PrIs) were assessed for size and stage. Training for visual skin assessment emphasized identification of stage 1 PrIs and deep tissue injury (DTI) because these conditions may be difficult to detect. Skin discoloration severity was graded as slight (pink or slight redness in persons with light skin tones and increase in normal skin color in persons with dark skin tones), minimal (redness in persons with light skin tones and deepening of normal skin color in persons with dark skin tones), moderate (bright redness in light skin tones and purple in dark skin tones), or severe discoloration (dark red to purple in light skin tones and black to blue-grey in dark skin tones). In persons with light skin tones, blanchability based on finger palpation was defined as blanchable or non-blanchable; blanching was not considered for persons with dark skin tones. Stage 1 PrIs were defined as skin discoloration with severity of minimal or greater. PrIs more severe than Stage 1 were classified using the NPIAP's 2019 classification system. For skin that demonstrated none of the above visual characteristics, the assessment was considered normal skin. The presence or absence of scar tissue, dry skin, rashes, skin tears, tattoos, and extensive or thick hair was also recorded.

*Subepidermal Moisture Measures.* Subepidermal moisture (SEM) was measured at each anatomic location on clean dry skin using the Provizio ® SEM Scanner (BBI LLC, Bruin Biometrics, Los Angeles, California, US) dermal phase meter. Using dielectric parameters, the

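### The visual definition of an intraoperative acquired pressure injury does not require the site to be clear before surgery; secondarily, the day-2 and day-3 percentages are best read as inpatient prevalence, not incidence

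*Combined protocol and SAP*

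**What the plan says.** **Visual definition.** Under Skin Assessments, the paragraph defining intraoperative acquired injury gives two rules. The visual rule reads "First, as erythema/skin discoloration of minimal or greater severity by visual skin assessment". It is the same threshold the Visual Skin Assessment paragraph uses for any Stage 1 injury: "Stage 1 PrIs were defined as skin discoloration with severity of minimal or greater". The second rule, for subepidermal moisture (SEM), subtracts the pre-operative value and asks for a change of at least 0.6 pF.

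**Pre-operative data.** The same section states "Research staff collected visual skin assessment and sub-epidermal (SEM) measures for all participants" at the face, chest and iliac crest, before and after surgery. The exclusion criteria under Recruitment do not mention existing discoloration.

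**Analysis.** The Study Analysis Plan names "The two outcome measures, IAPrI incidence by visual assessment and SEM Deltas indicative of PrI" and compares the percentage of participants affected, using the definitions already given, by Fisher's exact test "for initial post-operative assessment and postoperative days 2 and 3 assessments". It adds: "There were insufficient participants to evaluate postoperative days 4 and 5". Daily assessment ran to day five but ended earlier if the participant was discharged. Two other sentences could bear on a cumulative outcome: a regression comparing participants "who did and did not develop skin damage or IAPrIs controlling for group", and "Cochran Mantel-Haenszel statistics were used to compare the groups". Neither states a time window or a denominator.

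**The concern.** There are two separate issues, and the first matters more.

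**New versus existing lesions.** The outcome is meant to capture injury acquired during surgery, but the written visual rule cannot tell a new lesion from one recorded beforehand. The dressing went on after the pre-operative assessment, so it could not have prevented a lesion already seen then. Counting such lesions adds the same background to both arms if they are balanced, and a spurious difference if they are not. The available text states no allocation method, so balance cannot be presumed. The SEM outcome is already a change score and is not affected.

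**Incidence versus prevalence.** The visual outcome is called incidence. On days 2 and 3, however, only participants still in hospital can be assessed, and nothing says how discharged participants or resolved lesions are counted. A reader could take those percentages as the share of operated participants who developed an injury. The label is attached to the visual outcome only, but the inpatient denominator applies to the SEM results as well.

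**Working it through.** The documents give no sample size, event rate, alpha or power, so there is no figure of the plan's to reproduce. The reading comes from the text; every rate below is an assumption chosen for illustration. Power is exact, for a two-sided Fisher test at 0.05 with 30/50/100 operated per arm.

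**1. Reading the definition.** The two rules stand in one paragraph. The SEM rule refers to the pre-operative value; the visual rule does not. The analysis section adopts the definition without adding a baseline condition, and eligibility does not remove affected participants. Followed as written, a site graded minimal or worse both before and after surgery is a case.

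**2. Equal pre-existing discoloration.** Let *p* be the new-lesion risk and *b* the share with discoloration beforehand that persists, independent of *p*.

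- The written rule reads b + (1−b)p, so the difference shrinks by the factor 1−b.
- New lesions in all operated participants read (1−b)p.
- Participants clear beforehand read p, on about n(1−b) per arm.

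With p = 40% (control) and 15% (dressing), b = 10% gives 0.10 + 0.90×0.40 = 46.0% and 0.10 + 0.90×0.15 = 23.5%. With b = 20% the readings are 52.0% and 32.0%.

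| b | Written rule | New, all operated | Clear beforehand |
|---|---|---|---|
| 0% | 49/76/97% | same | same |
| 10% | 35/59/90% | 42/69/95% | 43/70/96% (n = 27/45/90) |
| 20% | 26/46/79% | 35/61/91% | 40/64/93% (n = 24/40/80) |

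**3. Unequal pre-existing discoloration, no true effect.** Take p = 25% in both arms, b = 15% in controls and 5% with the dressing.

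- Written rule: 0.15 + 0.85×0.25 = 36.3% vs 0.05 + 0.95×0.25 = 28.8%, a false 7.5-point benefit.
- New lesions in all operated: 0.85×0.25 = 21.3% vs 0.95×0.25 = 23.8%, a false 2.5 points the other way.
- Clear beforehand: 25% vs 25%.

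Of the three, only the comparison among clear sites shows no false difference here.

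**4. Days 2 and 3.** If affected and unaffected participants remain in hospital with probabilities k1 and k0, inpatient prevalence is p·k1 / (p·k1 + (1−p)·k0).

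- Same retention in both arms (k1 = 75%, k0 = 50%), p = 40% vs 15%: controls 0.30/0.60 = 50.0%, dressing 0.1125/0.5375 = 20.9%. The percentages move, but the odds ratio stays at 3.78, so no false association arises.
- No true effect (25% in both), k1 = 70% in both, k0 = 60% in controls but 55% to 40% with the dressing: 28.0% vs 29.8% to 36.8%, so the dressing looks 1.8 to 8.8 points worse.
- Resolution: a 30% cumulative risk reads 22.5%, 15% or 7.5% on a later day if 25%, 50% or 75% of lesions have resolved.

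**5. Power on days 2 and 3 can go either way.** If every lesion shows at the initial look, that test has 49/76/97%, and day 2 with 75/50 retention has 38/56/89%. If a quarter of lesions appear later, the initial test (30.0% vs 11.25%) has 32/57/89%. With all lesions visible on day 2, that day's test has 38/56/89% under 75/50 retention and 40/65/94% under 80/70 retention.

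**The case against.** **The intent is evident.** The words acquired, incidence and develop all point to new lesions, and pre-operative skin was inspected, so the investigators may well have removed baseline lesions in practice. This stands as a statement about intent. It does not supply the rule: the definition the analysis relies on has no baseline condition, whereas the neighbouring SEM rule has one. Nor do the documents show that any participant had discoloration beforehand, so an actual error in the counts cannot be asserted.

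**The day-2 and day-3 point is largely a matter of labelling.** The plan does say which assessments are compared. With equal retention the odds ratio is unchanged, and false differences need retention that differs by arm, which is assumed here. That stands, and it is why this part is secondary.

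**Stronger readings to avoid.** A reader might infer that discharge has biased the group comparison; the documents neither show nor exclude this. A reader might infer that the later tests must have less power than the initial one; step 5 shows this fails when some lesions appear late. A reader might also conclude that the whole result should rest on the initial assessment. That is a trade-off: it is scheduled for everyone and is not subject to discharge selection, but a single early look can miss late lesions, and the plan ranks no time point.

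**Conclusion.** The main point holds on the text: as written, persisting pre-operative discoloration counts as intraoperative acquired in the visual outcome, including at the initial assessment. Its effect on this trial cannot be sized, because no rates or group sizes are given. Under the assumed 40% vs 15%, 10% pre-existing discoloration lowers power at 50 per arm from the 70% available among clear sites to 59%; under the assumed 15% vs 5% imbalance it produces a 7.5-point benefit from no effect.

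The secondary point holds as the best-supported reading rather than a stated fact. The inpatient denominator is inferred from assessment ending at discharge and from the remark on days 4 and 5. The consequence is one of interpretation: those percentages are not incidence in all operated participants, and no cumulative comparison between groups is clearly specified.

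**What to change.** 1. **Definition and main comparison.** Count a visual injury only where discoloration graded minimal or worse was absent at that site pre-operatively. Compare groups among participants whose site was clear beforehand. Give new lesions in all operated participants as a sensitivity analysis, and tabulate pre-operative discoloration by site and arm. If baseline lesions were in fact already removed, say so and state the rule used.
2. **Days 2 and 3.** Report these as prevalence among inpatients, with numbers assessed by arm and day, and do not interpret them as incidence. Note that the initial assessment is the comparison not subject to discharge selection.
3. **Optional.** Add any new injury through day 3 or discharge in all operated participants as a supportive analysis, with the number of looks per participant by arm.

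**Cost.** Wording and a short re-analysis of data the protocol says were collected. The new-only rule misses true new injury at a site already discolored, and the clear-site comparison drops some participants. The optional cumulative measure still depends on length of stay. The plan is written in the past tense, so every change must be reported as post hoc.

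### The risk-factor logistic regressions have no small-sample provision; if IAPrI cases are few or a binary factor is uncommon, their odds ratios can be inflated or infinite

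*Combined protocol and SAP*

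**What the plan says.** All the analysis text is in the Study Analysis Plan section of the combined protocol and SAP.

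- **Group comparison.** "Using Fisher's Exact test statistics, the percent of participants with IAPrI on face, chest, and iliac crest as defined above were compared", at the initial post-operative assessment and on two later days. A further sentence reads "Cochran Mantel-Haenszel statistics were used to compare the groups", with no strata named.
- **Risk factors.** The method is given as "Using binary logistic regression analyses, demographic, medical and surgical factors were compared for prospective participants". The outcome and the adjustment are described in these terms: "who did and did not develop skin damage or IAPrIs controlling for group". The factors named are "hospital length of stay, surgery length, body mass index (BMI), and skin tone", but the wording presents them as examples, so the list is open.
- **Numbers.** The only remark on small numbers is "There were insufficient participants to evaluate postoperative days 4 and 5".
- **Events.** Under Skin Assessments, IAPrI has two definitions: "First, as erythema/skin discoloration of minimal or greater severity by visual skin assessment", and a subepidermal moisture criterion, "SEM Deltas greater than or equal to 0.6pF were considered indicative of IAPrIs".

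The plan does not say how the logistic models are estimated, whether factors enter together or one at a time, how many parameters a model may carry, or what happens if a cell is empty or a fit diverges. The document gives no sample size, event count or event rate.

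**The concern.** Binary logistic regression without further qualification normally means maximum likelihood. With few events per parameter, that estimator is biased away from zero on the log odds scale. If a factor, or a combination of factors, splits cases from non-cases perfectly (separation), at least one estimate is infinite. Software then prints a very large coefficient with an uninformative Wald interval, or drops the term.

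Two routes lead there: few cases overall, or a binary factor carried by few participants. The second can arise even when cases are common. The Medical Record Data section abstracts some binary items that could be uncommon, such as peripheral vascular disease and intra-operative vasopressor use. The open factor list does not exclude them.

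At stake are the reported risk factors for IAPrI: an odds ratio could be overstated, or a factor could disappear from the results because its fit failed.

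**Working it through.** **Status of the figures.** The document has no figure to reproduce. Every N, event rate, prevalence and effect below is an assumption, chosen to show a range. Separation was tested by linear programming.

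**1. Joint model.** From the plan: group plus the four named factors, so 5 covariates. Assumed: 400 data sets per cell; N = 50, 100 or 200; event rates 5, 10, 20 and 40%; 1:1 groups with group OR 0.5; three standardised continuous factors with ORs 2, 1.5 and 1.5; a binary skin-tone term with 20% prevalence and OR 2. Events per covariate = events / 5. The estimates are for the continuous factor with true OR 2, that is log OR ln 2 = 0.69.

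| Events (about) | Events per covariate | Separated | Mean ML log OR, separated sets excluded | Median ML OR, same sets |
|---|---|---|---|---|
| 2.5 | 0.5 | 71% | 1.58 | 2.83 |
| 5 | 1 | 33–34% | 0.85–1.02 | 2.08–2.29 |
| 10 | 2 | 5–8% | 0.75–0.89 | 2.04–2.19 |
| 20 | 4 | 0.3–1% | 0.74–0.84 | 2.08–2.18 |
| 40 | 8 | 0% | 0.73–0.75 | 2.06–2.12 |
| 80 | 16 | 0% | 0.72 | 2.04 |

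The mean bias at about 5 events is 0.85 − 0.69 = 0.16 to 1.02 − 0.69 = 0.33. At about 40 events it is 0.04 to 0.06. From 5 events upward the median is much nearer 2, so the inflation sits largely in a long upper tail. Firth estimates averaged 0.62–0.69 in every cell and were finite in separated data sets.

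A second set of runs used group, three continuous factors and one 15% binary factor, with a log OR of 0.60 for every factor and a group OR of 1.0 or 0.5 (1,000 data sets). Separation was 31–35% at N = 60 with 6 events, 16–20% at N = 100 with 8, 4–5% at N = 100 with 14, and under 1% at N = 100 with 25. At 25 events the mean ML estimate was 0.65–0.67 against 0.60.

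**2. Group plus one factor.** The plan can also be read this way. With one continuous factor, separation was 8–12% at 6 events, 3–5% at 8 and under 1% at 14. With one binary factor (OR 2, group OR 0.5, 600 data sets per cell) it was:

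| N, events (about) | 15% prevalence | 10% | 5% |
|---|---|---|---|
| 60, 6 | 26% | 39% | 62% |
| 100, 11 | 9% | 19% | 39% |
| 100, 21 | 0.7% | 3.5% | 20% |
| 100, 40 | 0.2% | 1.3% | 15.5% |

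A separate check at N = 60 to 100 gave the same pattern: about 20–53% at N = 60 and 4–26% at N = 100 with 10% events, and still about 3–15% for a factor of 8% prevalence at a 40% event rate. Single cells should be read as approximate.

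**3. Hand check of the second row.** The estimate diverges when no carrier of the factor has an event. With m carriers, each at risk q, that probability is (1 − q)^m. Take a 10% risk in non-carriers and OR 2: odds = 2 × 0.10/0.90 = 0.222, so q = 0.222/1.222 = 0.182. At N = 100:

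- m = 15: 0.818^15 = 0.05
- m = 10: 0.818^10 = 0.13
- m = 5: 0.818^5 = 0.37

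The simulated 9%, 19% and 39% are somewhat higher, as expected, because m varies and the group term can separate too.

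**The case against.** The strongest reply is that nothing in the document shows that cases were few. Fisher's test is valid at any count, so choosing it does not establish sparsity. The remark on days 4 and 5 concerns participants still available. Assessment stops at discharge, which is explanation enough. The visual definition has a low threshold, eight locations are examined, and the regression outcome adds skin damage to IAPrI, so events could be common. Three of the four named factors are naturally continuous. The long list under Medical Record Data is a list of abstraction fields and specifies no model. All of this stands.

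A reader might infer that an exact test for groups beside ordinary regression for risk factors is inconsistent. It is not: Fisher's test cannot adjust for group, so the two methods answer different questions. A reader might also infer that a diverging dressing coefficient would undermine the treatment comparison. That comparison rests on Fisher's test, supplemented by the Cochran Mantel-Haenszel statistics, and does not depend on the regression.

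The reply does not remove the gap. The plan offers no event count to reassure the reader and no rule if a fit fails, and common events do not protect an uncommon binary factor (15.5% separation at 5% prevalence with about 40 events).

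**Conclusion.** The concern holds as a conditional one of low severity. The models have no small-sample provision and an open factor list. With roughly 10 or fewer cases, or a binary factor under about 10% prevalence, maximum-likelihood odds ratios can be biased away from 1 or infinite. With about 25 or more events and common or continuous factors, the effect is minor.

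The document does not support the stronger statement that this plan does produce inflated or infinite odds ratios. That would require the number of cases, the number of parameters per model and the factor prevalences, none of which is given. Maximum likelihood is itself the default reading of the text and is not stated there. The thresholds rest on the assumed designs above and are guides, not sharp limits. Only the risk-factor results are affected.

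**What to change.** Fit the same risk-factor models, adjusted for group, by Firth penalised logistic regression, and take 95% confidence intervals and tests from the profile penalised likelihood. For each model, report the number of events and the number of parameters, and say whether factors were entered jointly or singly.

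The cost is a change of estimation option and a few reported counts, with no new data. The price is slight shrinkage, negligible when events are plentiful. Firth fitting keeps estimates finite and stayed near the true value in most settings examined, though not in all of the sparsest ones with a rare factor. It cannot make a nearly empty cell informative, which is why the counts should be reported beside the estimates. Exact logistic regression is a reasonable alternative. Limiting models to pre-named factors is not proposed here, because the plan contains no closed list to limit them to.
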